Dose Escalation Safety Lead-In and Mid-Study Interim Safety Analysis	
Dose Escalation Safety Lead-In
 
1. If, at any time, 1 or more of the first 3 safety-evaluable patients experience grade 3 or higher treatment-associated adverse events within the first 30 days of initiation of treatment, then no further patients will be enrolled at the current dose level.2. After 6 patients have been enrolled on study, enrollment will be halted for 30 days for completion of the dose escalation lead-in safety analysis. If 0-1 patients experience grade 3 or higher treatment-associated adverse events within the first 30 days of initiation of treatment, then additional patients may be enrolled at the next dose level.3. If enrollment is halted at any time during the lead-in period due to treatment-associated adverse events, the UCSF DSMB will review all available safety data with the Principal Investigator. Based on this review, study discontinuation or reduction of the epacadostat dose may be recommended. No further patients will be enrolled on study without the approval of the DSMB. If the DSMB allows additional patients to enroll, the lead-in period will be repeated at the new dose level with a maximum of 6 additional patients enrolled prior to follow-up safety analysis. At the discretion of the DSMB, patients who are currently on study may continue treatment at the reduced dose level.4. Patients who discontinue treatment on study within 30 days of initiation of therapy for reasons other than treatment-associated toxicity will be deemed inevaluable for safety and replaced for safety analysis. 
Mid-Study Interim Safety Analysis (Stage 1)
 
Enrollment will also be halted for 30 days for interim safety analyses after a total of 30 safety-evaluable patients have initiated treatment on study in both Arms A and B. Patients who discontinue treatment on study within 30 days of initiation of therapy for reasons other than treatment-associated toxicity will be deemed inevaluable for safety and replaced for safety analysis. The study will be discontinued under the following circumstance:
 
1. On-study occurrence of 3 or more Grade 4 (life threatening) serious adverse events (SAEs) or deaths, which are deemed at least possibly related to the study agent.2. Based on the review of data the DSMB has serious concerns about the safety of patients on the study. In addition to stopping the study, the DSMB may recommend that the epacadostat dose for all patients be de-escalated for all current and future patients or cessation of further patient accrual.

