--	---

Duration of Therapy	
Dose Escalation Safety Lead-In Phase: 6 patients will receive triplet therapy for 30 days at Dose level 0. After 30 days of therapy, if those patients do not experience a DLT, an additional 6 patients will be enrolled at the next Dose level, Level 1 which will increase epacadostat to 600 mg for 30 days, tavo-EP and pembrolizumab will not be dose escalated. If no patients experience a DLT at 600 mg, that will be the dose level of epacadostat used in Stage 1, for both Arms A and B.
 
Dose Expansion Phase, Stage 1, Arm A: Patients will receive triplet therapy for 12 months or until the development of an unacceptable treatment associated toxicity or confirmed progression. After 12 months of therapy, patients will enter the follow-up phase for the next 24 months. Patients with disease progression during the follow-up phase will have access to 12 additional months of triplet therapy. Patients who are eligible for treatment on study but who have experienced regression of all previously accessible lesions may continue on pembrolizumab and epacadostat without tavo-EP.
 
Dose Expansion Phase, Stage 1, Arm B: Patients will receive combination therapy for 12 months or until the development of an unacceptable treatment associated toxicity or confirmed progression. After 12 months of therapy, patients will enter the follow-up phase for the next 24 months.
 
Dose Expansion Phase, Stage 2: Depending on the results of the clinical data in Stage 1, Stage 2 will enroll up to an additional 26 patients accordingly:
 
If there are at least ≥ 3 responses in 15 patients, in either Arms A or B, up to an additional 26 patients (13 patients in Arm A and 13 patients in Arm B) will be enrolled in the respective treatment arms.

Duration of Follow up	Patients will be followed at 3 month intervals for toxicity and radiographic imaging 1) until start of a new anti-cancer treatment, (2) until 30 days after documented disease progression, (3) until death, or (4) until 36 months from the initiation of treatment on study, whichever comes first. Each subject will be followed for overall survival until death, withdrawal of consent, or the end of the study, whichever occurs first.
Duration Of Study	Study accrual will be sufficient to assess the primary endpoint within 24 months from the time the study opens to accrual.

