- f. Alkaline phosphatase $> 2.5 \times$ ULN. Note: Subjects with 1) bone metastases and GGT $< 2.5 \times$ ULN may enroll if the alkaline phosphatase is $< 5 \times$ ULN.
- g. Total bilirubin above $1.5 \times$ the institutional ULN AND conjugated bilirubin $\geq 2.0 \times$ ULN.
- h. International normalized ratio (INR) or prothrombin time (PT) $> 1.5 \times$ ULN.
- i. Activated partial thromboplastin time (aPTT) $> 1.5 \times$ ULN.

Table 3-1: Study Calendar

Period/Procedure	Screening	Cycle 1 (42 days)				Cycle 2+ (42 days)				Safety Follow-Up	
Study Day/Visit Day	-28 to 0	1	5	8	22	1	5	8	22	30 days from Last Dose	
Informed Consent											
Informed consent	X										
Clinical Procedures											
Medical history ¹	X										
Medication review	X	X				X	X			X	X
Physical exam	X	X				X	X			X	X
Vital signs ²	X	X	X	X	X	X	X	X	X		
Performance status ³	X	X				X	X			X	X
AE assessment ⁴		X				X	X			X	X
Treatment: Dose Escalation											
Safety Lead-In and Stage 1 and Stage 2, Arm A											
tavo-EP		X	X	X		X	X	X			
Pembrolizumab		X			X	X			X		
epacadostat	Continuous oral or per G-tube dosing										
Treatment: Stage 1 and Stage, Arm B											
tavo-EP		X	X	X		X	X	X			
Pembrolizumab		X			X	X			X		
Biospecimen Collections											
Screening Labs ⁵	X										
Safety Labs ⁶		X			X	X			X		X
ECG ⁷	X					(X)					
Archival Specimen Collection	X										
Fresh biopsy ⁸	X					X					X
Research Blood (mandatory) ⁹		X				X					X
Research Blood (optional) ⁹						X			X		
Tumor Assessments											
Tumor measurements ¹⁰	X					(X)					

- ¹ Medical history includes any conditions resolved within 6 months of enrollment as well as surgeries and therapies related to the treatment of melanoma and any residual toxicity.
- ² Includes blood pressure (systolic and diastolic), respiratory rate, heart rate and temperature. Height only required at screening. Weight only required at screening and day 1 of each cycle.
- ³ ECoG
- ⁴ CTCAE version 4
- ⁵ Screening labs include CBC with platelets and differential, LFTs (AST, ALT, total bilirubin, alkaline phosphatase), PT, PTT, electrolytes, BUN, creatinine, glucose, ionized calcium, lipase, amylase, HBsAg, HCV RNA quantitative
- ⁶ Safety labs include CBC with platelets and differential, LFTs (AST, ALT, total bilirubin, alkaline phosphatase), electrolytes, BUN, creatinine, glucose, ionized calcium, lipase, amylase
- ⁷ ECGs will be performed at screening and on day 1 of each odd numbered cycle excluding cycle 1.

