4.2 Dose Expansion Schedule

Table 4-2: Dose Expansion Arms in both Stage 1 and 2

	Treatment Arms	N	Epacadostat	pembrolizumab	tavo-EP
Arm A	tavo-EP, pembrolizumab ad epacadostat	28*	MTD - as determine by dose escalation	200 mg via IV. Days 1 and 22 of each cycle for 6 weeks (42 days)	1/4 tumor volume at concentration of 0.5 mg/mL ¹ given intratumoral on Days 1, 5, 8 of each cycle for 6 weeks (42 days)
Arm B	tavo-EP and pembrolizumab	28			

*Patients in the dose escalation safety lead-in will have an opportunity to participate in Stage 1, Arm A per Investigator's discretion.

Rationale for cohort expansion: In the dose expansion cohorts, we will determine the tolerability of this combination, the recommended phase II dose (RP2D) and preliminary efficacy in 56 evaluable patients with recurrent or metastatic squamous cell carcinoma of the head and neck with tumors. Hence the cohort expansion warrants the confirmation of tolerability of this combination, was deemed safe will be pursued for further patients.

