4.3 Dose Limiting Toxicity (DLT) and Maximum Tolerated Dose (MTD)

If DLT is encountered during the first cycle, the following rules (see table below) will be applied. If no DLT is encountered at a given dose level, escalation will be continued to the next higher dose level. If no DLT is found at the highest cohort, this cohort will be considered the recommended Stage 1 dose for epacadostat.

Table 4-3: Dose Escalation Decision Rules - DLT and MTD

Number of Patients with DLT at a Given Dose Level	Escalation Decision Rule
0 out of 3	Escalate dose to next higher dose level
1 out of 3	Enter at least 3 more patients at this dose level If 0 of these 3 additional patients experience DLT (1 of 6), proceed to the next dose level If 1 or more of the 3 additional patients suffer DLT (2 of 6), then dose escalation is stopped and this dose is declared the maximal administered dose (highest dose administered) Determination of the MTD will continue at the next lowest dose cohort, at which an additional 3 patients will be added, for a total of 6 (unless that cohort already has 6 patients)

≥ 2 out of 3	Dose escalation will be stopped This dose level is declared the maximum administered dose The next lower cohort will be expanded to 6 patients If < 1 experience DLT, this dose is the maximal tolerated dose (MTD)
≤ 1 out of 6 at highest dose level below the maximum administered dose	This is generally the recommended Phase 2 dose At least 6 patients must be entered at the recommended Phase 2 dose

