4.3.1 Dose Limiting Toxicity

Adverse Events and other symptoms will be graded according to the NCI Common Terminology Criteria for Adverse Events Version 4.03 (NCI, CTC web site <http://ctep.info.nih.gov>).

A DLT will be defined as any one of the following adverse events occurring during Cycle 1 when association to therapy that is part of this study is related or possibly related:

1. Hematologic dose-limiting toxicity

- Grade 4 neutropenia lasting for ≥7 days in duration.
- Febrile neutropenia of any grade
- Grade 4 thrombocytopenia ($\leq 25.0 \times 10^9/L$) lasting for ≥7 days in duration.
- Grade 3 thrombocytopenia complicated by clinically significant bleeding and/or requiring platelet or blood transfusion

2. Non-hematologic dose-limiting toxicity

This will be defined as any Grade ≥3 non-hematologic toxicity, which is clinically meaningful and related with the specific **EXCEPTION** of:

- Any grade alopecia
- Grade 3 total hyperbilirubinemia if <35% is direct component
- Grade 3 transient ALT/AST elevation
- Grade 3 rash, nausea, vomiting or diarrhea for ≤ 3 days or is not properly managed with optimal supportive care
- Grade 3 lab abnormalities must be clinically significant, meaningful and dose related.

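### The lead-in escalation decision can be made at 30 days, up to 12 days before the last patient(s) complete the DLT period (Cycle 1, best read as 42 days)

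*Combined protocol and SAP*

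**What the plan says.** **DLT period.** Section 4.3 introduces Table 4-3 with "If DLT is encountered during the first cycle, the following rules (see table below) will be applied". Section 4.3.1 says "A DLT will be defined as any one of the following adverse events occurring during Cycle 1". Neither gives a number of days.

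**Cycle length.** Table 3-1 (Study Calendar) heads its column "Cycle 1 (42 days" and lists the Dose Escalation Safety Lead-In among the treatments it schedules. The synopsis (Study Design) gives lead-in tavo-EP on a six-week schedule, which agrees. Table 4-2 also uses 42 days, but for the expansion arms. Table 4-1, the dose-escalation table, refers to cycles of 28 days.

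**Decision time.** The synopsis (Duration of Therapy) gives six patients the triplet at level 0 and continues: "After 30 days of therapy, if those patients do not experience a DLT, an additional 6 patients will be enrolled at the next Dose". The second cohort, at level 1, then receives 600 mg for 30 days, followed by "If no patients experience a DLT at 600 mg, that will be the dose level of epacadostat used in Stage 1".

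**Halt and replacement.** In the synopsis, once six patients are enrolled, "enrollment will be halted for 30 days for completion of the dose escalation lead-in safety analysis". Section 5.2 has the same 30-day halt. Both count grade 3 or higher treatment-associated events, not DLTs. Both replace "Patients who discontinue treatment on study within 30 days of initiation of therapy for reasons other than treatment-associated toxicity".

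**Authorization.** Appendix 2 requires a written report at dose escalation, listing any DLT, and written authorization from the DSMC Chair or a qualified alternate. It sets no wait until Cycle 1 ends.

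**The concern.** Three periods (28, 30 and 42 days) stand side by side and nothing reconciles them. If Cycle 1 is 42 days, a qualifying toxicity on day 36 in the last level 0 patient is a DLT under section 4.3.1. Under the synopsis, level 1 could already have opened on that patient's day 31. Section 4.3 read alone implies waiting for the cycle to end; the synopsis and the 30-day halt do not.

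At stake is whether the step from 300 to 600 mg BID is taken on complete DLT information. The lead-in's primary objective is the safety of the triplet, and section 4.3.3 itself warns that immune-related events may arise early or months later, so toxicity late in Cycle 1 is foreseeable.

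**Working it through.** The documents state no operating characteristic for the lead-in, so there is no figure of theirs to reproduce. The check is day arithmetic, followed by an illustration on stated assumptions.

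**Step 1: the gap.** Days of the DLT period still to run at the decision = max(0, window − 30).
- 42-day Cycle 1 (Table 3-1; six-week lead-in regimen in the synopsis): 42 − 30 = 12 days, and 12/42 = 28.6% of the window.
- 28-day cycle (Table 4-1): 28 − 30 is negative, so there is no gap.

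**Step 2: how many patients are affected.** Take six patients (synopsis) and a decision 30 days after the sixth starts. Accrual spacing is not in the documents, so three cases are shown. The cohort's total is 6 × 42 = 252 DLT patient-days.

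| Accrual (assumed) | Patients short of day 42 | DLT days still to run |
|---|---|---|
| 12 or more days apart | 1 | 12 of 252 (4.8%) |
| 7 days apart (follow-up 65, 58, 51, 44, 37, 30 days) | 2 | 5 + 12 = 17 of 252 (6.7%) |
| All together | 6 | 72 of 252 (28.6%) |

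**Step 3: effect on the escalation trigger.** The synopsis trigger is no DLT in six. Assume a true 42-day DLT rate q and constant hazard, so the chance of a DLT by day t is 1 − (1 − q)^(t/42).

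For q = 1/3:
- By day 30: 1 − (2/3)^(30/42) = 0.2515.
- A patient DLT-free at day 30 has a DLT on days 31–42 with probability (0.3333 − 0.2515)/(1 − 0.2515) = 10.9%.
- P(0 of 6), full follow-up: (2/3)^6 = 8.8%.
- Only the last patient cut: (2/3)^5 × 0.7485 = 9.9%.
- Weekly accrual: (2/3)^4 × (2/3)^(37/42) × (2/3)^(30/42) = 10.3%.
- All six cut: 0.7485^6 = 17.6%.

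For q = 0.25, the DLT probability by day 30 is 0.1857 and the single-patient late risk is 7.9%. P(0 of 6) is 17.8% with full follow-up, 19.3% with the last patient cut, 20.0% with weekly accrual and at most 29.1%.

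**Step 4: without constant hazard.** Let a fraction f of DLTs fall after day 30, with only the last patient cut and q = 1/3. Then P(0 of 6) = (2/3)^5 × [1 − (1/3)(1 − f)], which is 9.2%, 9.9% and 10.5% for f = 0.10, 0.25 and 0.40.

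The separate 30-day rule on grade 3 or higher events is not modelled. It would stop some of these cohorts.

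**The case against.** The best defence is that little turns on this.

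**Escalation is central.** A reader might infer that sites could reach different escalation decisions from the same data. The documents do not support that: Appendix 2 requires DSMC authorization, and the coordinating center confirms each patient's dose level. This stands. The ambiguity rests with one decision-maker.

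**Nothing is lost.** A reader might also infer that days 31–42 go unobserved. They do not. Patients stay on treatment, section 5.2 sets weekly safety calls during the lead-in, and Appendix 2 requires a participating site to report a DLT to the coordinating center within one business day. This stands too, but reporting after the decision does not delay the decision.

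**The Stage 1 dose.** It is tempting to say that the plan fixes this dose at day 30. The synopsis gives 600 mg for 30 days and then states a no-DLT condition with no day count; section 4.3 ties the dose to DLTs in the first cycle. The 30-day point is implied, not stated.

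**The trigger is strict.** With full follow-up, Table 4-3 (none of three, or one of three then none of three) escalates with probability 8/27 + (12/27)(8/27) = 42.8% at a DLT rate of 1/3, and 60.0% at 25%. Even the worst truncated case of the synopsis rule (17.6% and 29.1%) is well below that. This stands as a matter of size: the difference between the rules outweighs these 12 days. It does not settle when follow-up is complete.

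**Table 4-1 is the escalation-specific table, and 30 days covers its 28.** True, but the calendar names the lead-in and the lead-in regimen is six-weekly, so 42 days has the better support.

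**Conclusion.** The inconsistency is real, and on the better-supported reading it has a consequence: the stated 30-day rule allows escalation up to 12 days before the stated DLT period ends for the last patient(s). The same 30-day observation is implied, though not stated outright, before the Stage 1 dose is chosen. Neither DSMC authorization nor the 30-day rule on grade 3 or higher events closes the gap.

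The problem is one of decision timing, not of missing data. At an assumed DLT rate of 1/3 the chance of passing the trigger moves by about one percentage point (8.8% to 9.9%) if only the last patient is cut short, and to 17.6% at the extreme of simultaneous accrual. These sizes rest on an assumed DLT rate, event timing and accrual pattern, none of which the documents give. Twelve days is itself an upper limit, since preparing the report and obtaining authorization take some time. On a 28-day cycle the gap disappears, but the text would still need reconciling. Severity is minor to moderate.

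**What to change.** State the DLT period in days and use it throughout:
- Section 4.3.1: Cycle 1 (Days 1 to 42).
- Table 4-1: 42-day cycles.
- Synopsis (Duration of Therapy and the lead-in rules) and section 5.2: escalation, and Stage 1 dose selection after level 1, wait until the last patient in the cohort has completed Cycle 1, with the Cycle 2 Day 1 safety labs reviewed, or has had a DLT.
- Replacement rule in both places: extend from 30 to 42 days.

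The cost is amendment wording, up to 12 more days' pause per dose level, and an occasional replacement for a patient who leaves on days 31–42 for a non-toxic reason. No procedure is added: Table 3-1 already schedules safety labs on Cycle 2 Day 1, which is day 43. The last scheduled labs before a day-30 decision are those of day 22, the day of the second pembrolizumab dose.

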- ⁸ Fresh biopsy collection will be done at screening, Cycle 2 Day 1, and at progression/end of treatment. Additional biopsies may be performed if clinically indicated.
- ⁹ Research blood requirements are described in *Section 10*. Mandatory blood collection will occur on Cycle 2, Day 1; Optional sample collection will occur on Day 22 for Cycles 2 and beyond and then on Day 1 for Cycles 3 and beyond. Additional research blood acquisition, storage, and distribution information is provided in *Section 10*. Every effort shall be made to collect mandatory post-treatment (follow-up) research blood samples, but failure to collect this sample due to patient refusal or logistical constraints shall not constitute a protocol deviation or violation.
- ¹⁰ MRI, contrast-enhanced CT, or PET/CT imaging of the face, neck, chest, abdomen, and pelvis are required at screening and on day 1 of each odd-numbered cycle excluding cycle 1. Both clinical and radiographic measurements may be used. All superficial, clinically apparent lesions that cannot be adequately assessed radiographically (e. g. subcutaneous lesions) must be numbered and photographed with a metric ruler visible in each photograph. For photographed lesions with borders that are not clearly visible, investigators should trace the lesions' outline, making a solid line with a felt-tipped pen. Visible lesions should never be circled with a solid line but dashed or dotted lines may be used to distinguish these markings from the borders of otherwise invisible lesions. Tumor assessments will be made using RECIST version 1.1. IL-12 plasmid dosing may be based on the most recent tumor measurements and measurements need not be repeated immediately prior to each tavo-EP treatment.
- ¹¹ Epacadostat dose may be changed if indicated based on dose escalation safety run-in described below in Table 4-1.

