4.3.3 Treatment Modification – All Agents

Adverse events associated with treatment on study may be immune-related or not immune-related. Immune-related AEs (irAEs) may be predicted based on the nature of the compounds, their mechanism of action, and reported experience with immunotherapies that have a similar mechanism of action. Special attention should be paid to AEs that may be suggestive of potential irAEs. An irAE can occur shortly after the first dose or several months after the last dose of treatment. If an irAE is suspected, efforts should be made based on the investigator's clinical judgment to rule out neoplastic, infectious, metabolic, toxins, or other etiologic causes prior to labeling an AE as an irAE.

In some circumstances, it may be necessary to temporarily interrupt pembrolizumab, tavo-EP or epacadostat as a result of AEs that may have an unclear relationship to any individual study drug. If an interruption for an adverse event is necessary and the causative agent cannot be identified, all agents should be interrupted. Immune-related adverse events may also be attributable to epacadostat alone, pembrolizumab alone, tavo-EP, alone or the combination of two or three of these agents. If the event is clearly related to one of the agents, follow the instructions specific for that agent. If the event is related to more than one agent, follow the action taken instructions for each causative agent.

General supportive care recommendations to manage irAEs are detailed in *Table 4-4*. Additional treatment modification recommendations may be found in subsequent sections, in the pembrolizumab package insert, and in the investigator's brochures for epacadostat and tavo-EP.

Table 4-4: General Guidelines for Immune-Related Adverse Events

irAE Toxicity Grade	Withhold/Discontinue Agent(s)	Action Taken With Respect to Agent(s)	Supportive Care
Grade 1	No action.	Not applicable.	Provide symptomatic treatment.

Grade 2	May withhold agent per investigator's discretion.	Not applicable. Investigators discretion.	Consider systemic corticosteroids in addition to appropriate symptomatic treatment.

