4.5 Post-Treatment Follow-up

Patients will be followed for toxicity and radiographic imaging will be performed at 3 month intervals 1) until start of a new anti-cancer treatment, (2) until 30 days after documented

disease progression, (3) until death, or (4) until 36 months from the initiation of treatment on study, whichever comes first. Each subject will be followed for overall survival until death, withdrawal of consent, or the end of the study, whichever occurs first.

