4.6.2.3 Administration

Epacadostat will be administered orally BID every 12 hours without regard to food at the dose identified in this study. If a dose is missed by more than 4 hours, then that dose should be skipped, and the next dose should be taken at the next scheduled time point. All BID doses will be taken in the morning and evening, approximately 12 hours apart.

Subjects will begin treatment with epacadostat on cycle 1, day 1 of the study and will continue administration through the end of treatment. There is no priority to the order of administration of epacadostat, pembrolizumab, and tavo-EP when administered in combination; however, the dose of epacadostat should be taken as close to the regularly scheduled 12-hour dosing interval as possible.

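### Patients who stop study drug at progression, or start new therapy early, have no scheduled check for new toxicity after the 30-day visit

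*Combined protocol and SAP*

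**What the plan says.** The synopsis (Duration of Follow up) applies one set of end points to both toxicity and imaging at 3-month intervals: new anti-cancer treatment, then "2) until 30 days after documented disease progression, (3) until death, or (4) until 36 months from the initiation of treatment on study", whichever is earliest. Section 4.5 lists the same end points in looser grammar: "Patients will be followed for toxicity and radiographic imaging will be performed at 3 month intervals". Beyond those end points only survival continues: "Each subject will be followed for overall survival until death, withdrawal of consent, or the end of the study, whichever occurs first".

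Table 3-1 has one post-treatment safety column, headed "30 days from Last Dose". Sections 5.1 and 5.2 give 12-weekly evaluations to patients in follow-up who are off drug, and name no end point. Section 8 prohibits no therapy in post-treatment follow-up.

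On timing of toxicity, Section 4.3.3 says: "An irAE can occur shortly after the first dose or several months after the last dose of treatment". Section 7.6 summarises safety descriptively in all treated patients, by arm and overall.

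**The concern.** The plan says that immune-related events may first appear months after dosing stops, yet the rule that closes toxicity follow-up is the one that closes imaging. Ending scans soon after progression is reasonable. Ending the search for new toxicity at the same moment is a different decision, and the plan gives no reason for it.

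The consequence is uneven ascertainment. A new late irAE is looked for in a patient who is off drug without progression, and not in one who stopped because of progression or who moved quickly to another therapy. The late-event counts in Section 7.6 then partly reflect disease course. They could differ between arms if progression differed, even with equal late toxicity.

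**Working it through.** The plan states no figure to reproduce. The check compares dates.

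**Inputs**
- Imaging is required as follows: "are required at screening and on day 1 of each odd-numbered cycle excluding cycle 1" (Table 3-1, footnote 10). With 42-day cycles, the first on-treatment scan is on study day 2 × 42 + 1 = 85, and later scans are 84 days apart.
- Pembrolizumab is given on "Days 1 and 22 of each cycle for 6 weeks (42 days") (Table 4-2). Tavo-EP is given no later than day 8 of a cycle, so in Arm B pembrolizumab is the last agent dosed before a scan.
- Epacadostat dosing (Arm A) "will continue administration through the end of treatment" (Section 4.6.2.3), so the last dose falls at about the scan.
- Toxicity follow-up closes 30 days after documented progression (synopsis).
- The off-drug evaluation interval is 12 weeks = 84 days (Section 5.1), or 3 months (synopsis and Section 4.5).

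**Patient dosed on schedule and stopped at a progression scan**
- Arm A: 0 days from last dose to scan, so follow-up closes at 0 + 30 = day 30 after the last dose.
- Arm B: day 22 of one cycle to day 1 of the next is 43 − 22 = 21 days, so follow-up closes at 21 + 30 = day 51 after the last dose.

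The plan does not say from when the 12 weeks run, so each anchor has to be tried:
- From the last dose: 84 > 51 and 84 > 30, so no evaluation. With the ±3-day window of Section 3.4, 81 > 51 still holds.
- From the progression scan, or along the Table 3-1 calendar: the next evaluation is 84 days after the scan and follow-up closes 30 days after it, so no evaluation.

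The result is zero scheduled checks after the 30-day visit in both arms, whichever anchor is used.

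**Patient who starts new therapy**

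Follow-up closes on the start date. If that precedes the first off-drug evaluation, no check follows the 30-day visit. The calendar date of that first evaluation depends on the anchor.

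**Patients off drug without progression or new therapy (for contrast, counting from the last dose, with 30.44 days per month)**
- 12-month completer: 36 − 12 = 24 months = 730 days; 730 / 84 = 8.7, so 8 evaluations (24 / 3 = 8).
- Toxicity stop at month 2: 36 − 2 = 34 months = 1,035 days; 1,035 / 84 = 12.3, so 12 (34 / 3 = 11.3, so 11 at 3-month intervals).

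**Uncovered time for an assumed collection window after the last dose**

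| Window (days) | Days after the 30-day visit with no scheduled check |
|---|---|
| 60 | 60 − 30 = 30 |
| 90 | 90 − 30 = 60 |
| 120 | 120 − 30 = 90 |

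The documents give no rate of late irAEs, so these days cannot be turned into a number of missed events.

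**The case against.** The best counter-argument is textual. In Section 4.5 the numbered end points can be read as governing imaging alone, and Sections 5.1 and 5.2 promise 12-weekly evaluations off drug without a progression limit. On that reading there is only a wording conflict. It does not prevail, because the synopsis ties toxicity and imaging explicitly to the same end points. The ambiguity does mean that Section 5.1 needs aligning.

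Safeguards also exist. Section 11.5 follows adverse events until resolved. SAEs are reportable once the site becomes aware of them, with no stated post-dose limit. Appendices 2 and 3 list an event in a gene therapy study among the SAE criteria. This stands, and it narrows the loss to new events that nobody brings to the site, since none of these provisions schedules detection. It is also fair that ending toxicity follow-up at new therapy avoids confounded attribution.

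A reader might infer a general threshold, such as no check whenever progression comes within 54 days (84 − 30) of the last dose or new therapy within 84 days. The documents do not support this, because it requires counting from the last dose, while Section 6.1.1 refers assessments to Table 3-1. Take a patient whose last dose is on day 1 of cycle 2 (study day 43), stopped for toxicity, with progression found at the day-85 evaluation. That is 42 days after the last dose and 12 days after the 30-day visit (day 73), so one check has taken place.

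A reader might also infer that patients retreated late in follow-up lose post-treatment checks because of the month-36 cap. The text is silent on how follow-up runs after retreatment. Retreated patients have 3-weekly checks while on drug, and the 30-day visit is tied to their last dose.

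**Conclusion.** The point holds for two groups: patients stopped at a scheduled progression scan, and patients who start new therapy before their first off-drug evaluation. Neither has a scheduled check for new toxicity after the 30-day visit. The day-30 and day-51 closing dates assume dosing on schedule and stopping at the scan; the zero count there does not depend on the anchor. The contrast counts of 8 and 11 to 12 do assume counting from the last dose.

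The effect is confined to the descriptive summaries of Section 7.6. Lead-in dose decisions use 30-day or Cycle 1 windows, and efficacy is untouched. A reader might infer that the comparison between arms is biased. That goes too far: both arms have the same follow-up rule, Section 7.3 plans no formal test between arms, and an imbalance would arise only if progression or early new therapy differed. The number of missed events cannot be estimated. This is a cheap improvement that should be made, not a flaw in the trial's main conclusions.

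**What to change.** In the synopsis and Section 4.5:
- Keep the current end points for imaging, and the current 12-weekly evaluations for patients without progression. State that Section 5.1 follows the same rule.
- Add collection of new treatment-related SAEs and irAEs through a fixed window after the last dose of any study agent, regardless of progression or new therapy. Ninety days is an example; the length is an assumption for the sponsor to settle.
- Collect them by one contact at the end of the window, within survival follow-up. That follow-up has no visit schedule, so the contact date must be defined.
- Record the start date of any new anti-cancer therapy.

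In Section 7.6, tabulate events more than 30 days after the last dose separately, split into before and after the start of new therapy.

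The cost is protocol wording, plus one contact and one CRF page for each patient who leaves toxicity follow-up early. Late events are harder to attribute once new therapy starts; the split table makes that visible.
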